Page numbers from a sponsor's protocol/grant may be referenced in 1a and 1b.

In this question the IRB requires a brief introduction with supporting background information to describe your study. Do not include overly lengthy descriptions.

Protocol Title: Patterns and Prevalence of FDG extravasation in PET/CT scans

Investigator Initiated studies (i.e., the Principal Investigator has conceived, designed, and is conducting the research) are required to cite references in the response or should upload a referenced bibliography in the Attachments section.')">?HELP?*

With the commercialization of the first PET/CT scanner in 2001, this technology has played an ever increasing role in oncology, neurology, cardiology, and other applications. PET with 18F-FDG is used to diagnose, stage, and restage many cases of cancer; the accuracy ranges from 80% to 90% and is often better than that of anatomic imaging (1). Since the introduction of PET/CT, numerous studies have shown that this whole-body dual- technique imaging is better than PET or CT alone for staging and restaging most cases of cancer. The improvement in accuracy coupled with the convenience of presenting anatomic and functional information to physicians has rendered PET/CT the most important cancer imaging technique at present (2). Furthermore, the use of PET/CT has been advocated as a first-line imaging technique for whole-body tumor staging, restaging, and assessing response to therapy for different types of neoplasms (3). Since changes in FDG accumulation have been shown to be useful as an imaging biomarker for assessing response to therapy (4), PET/CT scanning through this combination of molecular and anatomical imaging is playing an ever increasing role as a way to quantitatively measure individual response to therapy and to even evaluate new drug therapies.

(5) The standardized uptake value (SUV) is commonly used as a relative measure of the labeled tracer uptake. The SUV is a ratio of the radioactivity concentration in an area of interest to the decay corrected amount of radiolabeled tracer divided by the patients weight in grams. It is believed that the two largest factors that influence SUV are: injected dose and patient size.

Primary factors that impact the delivered dose of FDG include: the uptake duration between injection and scan, residual syringe activity measurement, dose extravasation (also referred to as infiltration) near the injection site, patient weight measurement, clock synchronization for measuring dose assays and scanning, and data entry.

An extravasation or infiltration is a common problem that can occur when the radio-labeled tracer infuses the tissue near the venipuncture site, and can result from the tip of the catheter slipping out of the vein or passing through the vein. Additionally, the blood vessel wall can allow part of the tracer to infuse the surrounding tissue. As a result, the radio-labeled dose being delivered is inaccurate and as Kinahan has pointed out the accuracy of the calculated dose is critically important to the SUV calculations; errors in an SUV calculation in one assessment scan can severely impact patient treatment and research conclusions.

Extravasations/infiltrations may in fact contribute to the wide variability in researcher's efforts to characterize SUV thresholds for clinical decision making. Velasquez found that the "thresholds for metabolic response in the multicenter multiobserver non-QA settings were -34% and 52% and in the range of -26% to 39% with centralized QA". (6) In local practices and even in practices and research centers employing Quality Assurance checks, these issues with SUV calculations have left oncologists and researchers needing to see significant changes in SUV values to be somewhat assured they are making sound treatment decisions or reaching proper research conclusions.

While there is very little published information on FDG extravasation rates, they are not insignificant and the impact on SUV is not fully characterized. Thus, this study hopes to look at the frequency and patterns of extravasation episodes to better characterize their effect on SUV values.

AuthorJournalYearNInf RateComments
Hall, et al (7)
Ohio State UJ Nuc Med200619021% (39)Prospective
Krumrey, et al (8)
St Louis UJ Nuc Med200998
983% (3)
9% (9)Using automated injector

Protocol Title: Patterns and Prevalence of FDG extravasation in PET/CT scans

Manual injection [name], et al (9) St Louis UFrontiers in Oncology201140010.5% (42)Retrospective Silva-Rodriguez, et al (10) U Santiago, SpainMed Physics20141,36718%Retrospective

Please save frequently

b) Describe any animal experimentation and findings leading to the formulation of the study, if there is no supporting human data.

In oncology, whole-body PET/CT is typically performed from the head to the pelvic floor [7](eyes to thighs). The use of the term whole-body is misleading because the most commonly used field of view (FOV) for arms-up whole-body PET/CT protocols includes only the base of skull to the upper thighs and does not include the brain, skull, and large portions of both upper and lower extremities. In such FOV, the most commonly used site of injection, namely the antecubital fossa (inside of the elbow), is frequently not included in the imaging field. In the Frontiers in Oncology article, [name] also determined that based on the commonly used FOV at most PET/CT centers, that when infiltration is present, it may be unnoticed by clinicians in approximately 31% of the cases. (7) [See sources for citations on previous question]

Lucerno Dynamics, a privately held company in North Carolina, has also discovered that the static image may be incapable of reporting on the quality of FDG administration during the ~60 minute uptake period. Lucerno's system has been used in two investigational studies at two centers. At one center, the system was used with 8 patients for a total of 15 scans. At the other center, the system was used with 40 patients for a total of 85 scans. Similar rates of infiltrations were found to those described in the published articles. Based on this experience, Lucerno has found that infiltrations can partially resolve during the uptake period, so that even if they are visible in the PET image, the image may not reveal the extent of the infiltration. This could severely and negatively impact research and therapy decisions and thus patient outcomes.

The Lucerno devices (Lucerno ID) are nonsignificant risk devices that add only 2-3 minutes to the current standard of care PET/CT scanning process. Lucerno ID sensors are applied to the patient's skin before the injection of the radiotracer and are removed after the FDG uptake period and prior to the PET/CT imaging process. The Lucerno ID has the ability to identify infiltrations, whether they are within or outside the FOV of reviewing clinicians, and can alert clinicians before their patient undergoes a compromised PET/CT scan due to the infiltration. This technology can prevent patients from receiving the additional CT radiation exposure of a compromised scan, can save cost, and can improve patient outcomes by ensuring more accurate PET scan interpretation.

2. Purpose of the study

a) Provide a brief lay summary of the project in <200 words. The lay summary should be readily understandable to the general public.

PET (Positron Emission Tomography) images are used to help make patient management decisions in staging and treatment assessment, often after a cancer diagnosis.

Improper injections of PET tracers (dye) may occur approximately 15% of the time. This is known as extravasation or infiltration, and it compromises the doctor's ability to read the PET image. Often, the site where the tracer is injected into the vein (usually in the inside of the elbow) are not in the images taken, so reading physicians are unaware that an extravasation has occurred.

Protocol # 26741 [name]

Protocol Title: Patterns and Prevalence of FDG extravasation in PET/CT scans

Technology exists to capture time activity curves (amount of tracer in a location over a period of time) during the PET tracer uptake period (usually once the tracer is injected, the tracer circulates for 60 minutes prior to images), which can enable physicians to accurately detect extravasations. This information is currently unavailable to physicians reading routine PET/CT scans.

Time activity curves information gathered from these sensors during the circulation period appear to match the brief pictures taken approximately 70 minutes after the tracer injection.

This study will determine if these time activity curves correspond to PET images of the injection site taken during the tracer uptake period. If time activity curves correspond to PET images, they can be used to determine if the tracer was properly injected. If there was an improper injection, clinicians can be alerted to this fact and interpret the image with this additional information.

Page numbers from a sponsor's protocol/grant may be referenced in 2b and 2c.

b) List your research objectives (specific aims & hypotheses of the study).

The study will try to answer the following questions:

- •How often do infiltrations of FDG occur in routine PET/CT imaging?
- •Can the Lucerno ID (sensor device) accurately determine the presence or absence of an extravasation as confirmed by PET imaging?
- •Can patterns be identified in the conditions that tend to lead to extravasation?
- •Is there a way to quantify the impact of an extravasation on the injected dose, and thus the SUV calculation?

Our hypothesis is that the Lucerno ID device accurately captures dose extravasations. Data extracted from Lucerno ID may help quantify extravasation and, in so doing, may allow for developing correction factors for measured SUV.

Please save frequently

c) Describe the study design (e.g., single/double blind, parallel, crossover, control, experimental, observational, etc.). If the study is investigator-initiated, a timeline for individual subject recruitment, follow-up, and analysis for the study is required. Also, indicate if the subjects will be randomized.

Investigator initiated, non blinded, experimental, non-randomized study

d) If subjects will be given placebo, please justify placebo use. *?HELP?*

N/A

3. Study Procedures

a) N Is this project a multicenter study (i.e., same project is conducted elsewhere by a different investigator) OR does this study involve conduct of research at multiple sites?
 Is SLU acting as a coordinating center for other sites OR is the SLU PI a direct recipient of a federal grant for this research? If yes, complete and attach the Supplemental

Protocol # 26741 [name]

Protocol Title: Patterns and Prevalence of FDG extravasation in PET/CT scans

Application for Coordinating Center Activities.

Will the SLU site be participating in all parts/procedures/arms of the study?

If No, explain what SLU will NOT participate in:

Please save frequently

Page numbers from a sponsor's protocol/grant may be referenced in 3b, 3c, and 3d.

b) Describe all the procedures, from screening through end-of-study, that the human subject must undergo in the research project, including study visits, drug treatments, randomization and the procedures that are part of standard of care. Specify which procedures are for research and which are standard of care. Please note: The box below is for text only. If you would like to add tables, charts, etc., attach those files in the Attachment section (#16).

Patients will be identified once they arrive for their standard of care PET/CT exam. If it is determined there is time and a sensor device is available, a subject will be asked about interest in participation. If they are interested, an informed consent dialogue will occur between patient and engaged team member such as a PET technologist, physician, or research coordinator. The informed consent document will be signed and retained (behind two locks) by engaged members of the research team. This includes the PI, other investigators (MDs), engaged PET technologists and/or the research coordinator.

Once consent is obtained the patient will continue on with the standard of care screening process (name, DOB, height, weight, eating status, etc. will be obtained for the standard of care PET/CT exam). Lara Systems is planned for use once we get this system which is planned for the week of 10/17/2016. Our plan would be to still use the LD1 ID until we get the Lara device or as a back up if the Lara device is not working properly. Just before the radioactive FDG is injected, the four sensors (injection site, contralateral arm - similar position to injection site, liver, and over the subclavian area) on the Lucerno ID device will be placed on the subject by the PET/CT technologist. The device sensors will remain in place for the FDG uptake period (typically 60-90minutes). The patient will be lying on the scanning table or in a reclined chair for this uptake period, depending on the availability of the imaging table. During the uptake period, if the scanner and imaging table are available, the subject will have dynamic PET only images taken to correlate sensor data with imaging. This is not a necessary part of the protocol and will only be performed if the scanner is available. If the PET/CT scanner is not available, the sensors will be placed in the same locations and at the end of the uptake period, sensor only data will be retained. After the uptake time is complete, the sensors will be removed by the technologist and the patient will proceed on with their standard of care PET/CT imaging. The patient will not receive any extra radiation due to the study and should only add 5 minutes to the time of their PET/CT scan.

The study team will then upload the sensor data to a PC in the PET/CT department where it will be coded and sent to Lucerno Dynamics via a software for analysis. If requested, the coded PET data obtained during the uptake phase (no additional radiation involved with this imaging) will be complied and shared with Lucerno Dynamics. The patient will also be asked to complete a quick survey on the comfort of use for the Lucerno ID device. This coded paper survey will be shared with Lucerno Dynamics for further development of this device.

c) If the proposed study is a clinical trial where a drug, vaccine, device or other treatment is compared to a placebo group or comparison treatment group, what are the guidelines or endpoints by which early decisions regarding efficacy or lack of efficacy can be made? For example, it may be reasonable to stop enrollment on a study when efficacy has already been

Protocol # 26741 [name]

Protocol Title:

Patterns and Prevalence of FDG extravasation in PET/CT scans

clearly demonstrated, to avoid unnecessary enrollments of additional subjects. Alternatively, it may be reasonable to stop enrollment when it is clear that efficacy will never be demonstrated, given the statistical power of the study as designed. Describe the guidelines that are in place to assist in making these determinations, if relevant to the proposed study.

This study does not include a control group, so there will be no comparison or efficacy measured.

d) Describe how data analysis will be performed (statistical tests, methods of evaluating data) and indicate the smallest group/unit for which separate reporting will occur. For studies involving a questionnaire, if data and reliability information are available, please describe or provide references. For full board, unfunded studies describe sample size determination and power analysis. If none, please justify.

The coded data (information will have study number only) will be reviewed by Lucerno Dynamics individually after each patient to look for quality. The quality will be reviewed to assess the injection site data visually and with time activity curves. Interval analysis will be done once significant recruitment has been achieved and reported if seen fit by SLU and Lucerno Dynamics. The data will be reviewed to look at group data and injection quality.

Please save frequently

- e) State if deception (including incomplete disclosure of study purpose/procedures) will be used. If so, describe the nature of the deception and provide a rationale for its use. Also, describe debriefing procedures or justify a waiver of the requirement to debrief. NOTE: for studies using deception, an alteration of consent must be justified in the Informed Consent section of the protocol (#13) and the debriefing script/statement must be uploaded in the Attachments section (#16). See IRB Deception Guidelines.
- f) Is there an accepted standard of care and/or standard practice at SLU for the condition/disease/situation being studied? This information will assist in comparing the risk/benefit ratio of study procedures relevant to usual care that would be received outside of the research context. *?HELP?*

If yes, please describe the standard of care and standard practice at SLU for the condition/disease/situation being studied.

g) Does this study involve any diagnostic imaging, labwork or genetic testing that could Y result in clinical discovery (diagnoses, genetic mutations, etc.)? Note that this could include discovery that is expected (related to the research) or incidental (not related to research aims, but possible, like a mass/shadow found in imaging despite not looking for it).

If yes, please describe and include whether there are plans to share findings with study participants.

This would be rare as these are additional images in the same location as the standard of care images; however, this is always a possibility with additional imaging. If something unexpected or unknown is discovered on the images, the reading physician will review with the Primary Investigator and inform the referring physician.

Protocol # 26741 [name]

Protocol Title:	Patterns and Prevalence of FDG extravasation in PET/CT scans	

Is this study subject to the NIH Genomic Data Sharing Policy? h)

Ν

The NIH GDS policy applies to all NIH-funded research that generates large-scale human genomic data as well as the use of these data for subsequent research and includes: genome-wide association studies (GWAS), single nucleotide polymorphisms (SNP) arrays, and genome sequence, transcriptomic, metagenomics, epigenomic and gene expression data, irrespective of NIH funding mechanism. Click here for more specific examples.

* * * Radioisotopes or Radiation Machines * * *

You have not selected the Radioisotopes option in the General Checklist. If you would like to add Radioisotopes information, please select the option to enable this section.

4. Radioisotopes or Radiation Machines

In this section, investigators must enter all radiation usage associated with the protocol.

Important: Protocols that involve non-standard of care radioactive materials (which includes the terms "radioisotopes", "radionuclides", "radiopharmaceuticals", and "nuclear medicine studies", e.g., "PET", "MUGA", "Zevalin", and/or specific radionuclides such as "F-18", "Tc-99m", "Th-201", "I-131", "Ra-233", "Y-90", etc.) will receive review by the Radiation Safety Officer (RSO) and/or Radiation Safety Committee (RSC). In these cases, submission to the RSO/RSC should occur first, even before submission to IRB. For more information on how to submit for radiation safety review, see RSC instructions or contact the Radiation Safety Officer at [name].

- (1) It is the responsibility of the PI to assure the accuracy and completeness of the data submitted in this section, consistent with guidelines provided below. (2) For projects requiring radiation procedures, please refer to this guidance.
 - If applicable, list and quantify the radiographic diagnostic and therapeutic procedures associated with this protocol by clicking "Add" and adding to Table 1 below. (Includes X-ray, fluoroscopy, CT, a) radioactive materials, nuclear medicine, PET-CT, radiation oncology, accelerator, Cyber Knife procedures, etc.)

1. Radiation Procedure: PET/CT

2. Total number of exams:

3. Are the procedures being performed as a normal part of the clinical management for the medical condition that is under study SOC (Standard of Care)?

If yes, specify the number of exams for each listed procedure that are SÒC.

NOTE: If all procedures are SOC (i.e., #2 and #3 are the same), you are finished with this procedure box. If there are procedures that are NOT SOC, proceed with this section.

4. Are the procedures being performed because the research subject is participating in this project (e.g., extra CT scans, more fluoroscopy time, additional Nuclear Medicine Studies, etc.), i.e., Not Standard of Care?

Ν

€-PROTOCOL

PROTOCOL Biomedical Research Saint Louis University

Protocol # 26741 [name]

Protoco	Protocol Title: Patterns and Prevalence of FDG extravasation in PET/CT scans			n PET/CT scans	
5. I	DUKE Radiation Safety Cor Adult Patients: CLICK HER Pediatric Patients: CLICK Use of additional reference	er Procedure (mrems): tive dose for each procedure mmittee Website: RE. HERE. is that may provide a hi is University Hospital ar cified below. Hems): The Number of procedure	edure that is NOT Sometimes of accurate encouraged. All researches that are NOT SO	OC. You may use data from the gracy of radiation dose estimates eferences, including use of the	
7. I	References. Specify the res	ource/reference used f	or estimating the do	se for this procedure.	
b)	Total estimated research		₹\$\	N/A	
* Calculate from the table above by adding the Effective Dose Subtotals for all procedures.					
NOTE: Informed Consent Radiation Exposure Risk Statement- The applicant must insert the appropriate Informed Consent Radiation Exposure Risk Statement template language into the SLU IRB Informed Consent, inclusive of applying the total estimated research radiation dose specified in item b) from the table above, as instructed in the SLU IRB Informed Consent Template. Contact the IRB Office at [name] or [contact] with any questions.					
		* * * Devices	* * *		
5. Device	S				
a) Please list in the space below all investigational devices to be used on subjects during this study.					
b) Please list in the space below all FDA approved devices to be used on subjects during this study.					
FDA Approved Devices					

Protocol # 26741 [name]

PROTOCOL Biomedical Research Saint Louis University

Protocol Title: Patterns and Prevalence of FDG extravasation in PET/CT scans

Device Name		Provide IDE #. Documentation of IDE # required unless imprinted on sponsor protocol (attach in section #16).
Lucerno ID	Lucerno Dynamics	

1. **Device Name** Lucerno ID

Manufacturer 2.

Lucerno Dynamics

3. Describe the device to be used and attach the device manual in section #16.

Lucerno ID device is made by Lucerno Dynamics and is a lightweight sensor that can adhere to skin and obtain radioactive counts. Lara is also a device made by Lucerno Dynamics and is a lightweight sensor that can adhere to skin and obtain radioactive counts. The LD1 and Lara Lucerno devices (Lurcerno ID) are both attached to the subject in the same manner and are considered non-significant

Provide the PMA approval or 510(k) clearance 4. number or attach letters in section #16.

document titled 2015-02-17 NSR Determination signed.pdf

5. Does the research involve use of a commercially available device for an unapproved purpose?

This device research is: Note: Attach 6. documentation/justification in section #16. Exempt from IDE regulations, (submit required attachments) Non-Significant risk, (submit required attachments)

Significant risk, (submit required attachments)

The risk determination should be based on the proposed use of a device in an investigation and not on the device alone.

- Provide IDE #. Documentation of IDE # required 7. unless imprinted on sponsor protocol (attach in section #16). See Guidance.
- 8. Who holds the IDE? (Could be manufacturer, study sponsor, or an individual investigator acting as the 'sponsor').
- If a SLU Investigator is serving as sponsor-investigator of the IDE, click Yes to assure that the 9. additional FDA requirements will be followed.

Yes, the additional FDA requirements will be followed.

Drugs, Reagents, Chemicals, or Biologic Products * * *

6. Drugs, Reagents, Chemicals, Biologic Products, or Dietary Supplements, Vitamins, and Other Food Agents

Pilot

Phase II

Phase III

Phase I Phase IV

Not Phased

List placebo if it is considered a drug (contains more than inactive ingredients). For example, normal saline is considered a drug that should be listed, whereas placebo tablets are usually inert ingredients that do not need to be listed.

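### Objective 1 asks for the infiltration rate in routine PET/CT, but section 3(b) recruits at discretion, and the text at hand sets no order of approach and no record of patients passed over

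*Protocol*

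**What the plan says.** Protocol section 2(b) lists four questions. The first is "How often do infiltrations of FDG occur in routine PET/CT imaging", and the study title also promises prevalence. The third is "Can patterns be identified in the conditions that tend to lead to extravasation".

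Section 3(b) describes recruitment. The source population is fixed by "Patients will be identified once they arrive for their standard of care PET/CT exam", and the rule for approaching them is "If it is determined there is time and a sensor device is available, a subject will be asked about interest in participation". Patients who are interested then go through consent, and data collection is described only from that point on. The section does not say who decides that there is time, by what criterion, or in what order patients are considered. It describes no count of patients passed over or declining. Section 3(d), on analysis, speaks of reviewing group data and injection quality and names no denominator of eligible or approached patients.

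On context, section 1(a) states that "there is very little published information on FDG extravasation rates", and the lay summary in section 2(a) says that "Improper injections of PET tracers (dye) may occur approximately 15% of the time".

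**The concern.** A question about how often something happens in routine practice calls for a sample whose link to routine practice is known. The stated rule selects on two things tied to workload: spare time and a free device. The sensors stay on for the whole uptake period, which section 3(b) puts at typically 60 to 90 minutes, so free devices are likely to be scarcer when patients follow closely on one another. Following the rule as written would therefore tend to under-represent busy sessions.

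This matters for Objective 1 if busy sessions have a different infiltration risk. The protocol itself expects risk to vary with circumstances, since Objective 3 sets out to find the relevant conditions. Given how little the protocol says is published, the resulting rate is also likely to be read as a routine figure. Finally, the approach rule cannot be changed once recruitment is over, and reasons for passing a patient over cannot be recovered if nobody noted them.

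**Working it through.** **The texts side by side.** The target in 2(b) is routine PET/CT. The source population in 3(b), patients arriving for standard-of-care scans, matches it. The step that departs from it is the approach rule, which takes an unspecified subset by discretion. A second step, patient interest, follows. Neither step has a described record.

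**Can selection depend on the outcome?** No. Patients are approached on arrival, before FDG is injected, so nobody can be chosen because an infiltration occurred. Bias needs an indirect route: lack of time or of a device must be related to infiltration risk. Nothing in the protocol establishes or excludes that relation.

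**The 15% figure.** It can be checked against the literature table in 1(a), whose layout is broken and is read here in order. The counts are 39 of 190, 12 of 196 (two groups of 98 combined), 42 of 400, and 18% of 1,367, or 246.06. The sum is 339.06 of 2,153, or 15.7%, in line with the lay summary's approximate 15%.

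**Illustration of size.** Two inputs are assumed, because the protocol gives neither:

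- e = share of routine FDG patients enrolled
- k = infiltration risk in non-enrolled patients divided by risk in enrolled patients

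Starting from a routine rate of 15%, the enrolled rate is 0.15 / (e + (1 − e)k). At e = 0.5:

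- k = 2: 0.15 / 1.5 = 10%
- k = 1: 0.15 / 1 = 15%, no bias
- k = 0.5: 0.15 / 0.75 = 20%

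In the other direction, if the study observes 15% among enrolled patients, the routine rate is 0.15 × (e + (1 − e)k):

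| e | k = 0.5 | k = 2 |
|---|---|---|
| 90% | 0.15 × 0.95 = 14.25% | 0.15 × 1.10 = 16.5% |
| 80% | 0.15 × 0.90 = 13.5% | 0.15 × 1.20 = 18.0% |
| 50% | 0.15 × 0.75 = 11.25% | 0.15 × 1.50 = 22.5% |
| 20% | 0.15 × 0.60 = 9.0% | 0.15 × 1.80 = 27.0% |

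These are consequences of the assumptions, not estimates of bias in this study. They show that the share enrolled governs how much an unknown k could matter. A count would supply e and divide the non-enrolled by reason. It would not supply k.

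**The case against.** The strongest reply has four parts.

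First, no bias is shown. A reader might infer from the approach rule that the reported rate will be wrong. The documents do not support that: nothing in them links staff time or device availability to infiltration, the values of k above have no source, and k = 1 gives no bias at all. This stands in full.

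Second, a reader might infer that the representativeness of the rate would be beyond judgement. That also goes too far. The number of scheduled FDG patients may be recoverable from clinical records, which would give e. Characteristics of enrolled patients, such as height and weight, allow some comparison with outside populations. What would be lost is the reason each patient was passed over or declined.

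Third, the text at hand is partial. It ends in form section 6, while sections 13 and 16 are referred to but not shown. The 3(b) prompt asks for procedures that subjects undergo, so a log of non-participants need not appear there. This stands as well: the absence of an order or log is confirmed only for the text available. The discretionary condition itself is stated outright.

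Fourth, the study's hypothesis concerns whether the device captures extravasations, and the rate is one of four questions. Convenience enrolment may serve the accuracy question well enough. Objective 1 nonetheless asks for a rate in routine imaging, and the title does too. Reading routine as standard-of-care scans identifies the source population but leaves open which of those patients are taken. That the study is not multicentre limits generalisation in any case. It does not excuse avoidable selection within the site.

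**Conclusion.** The point holds as a cheap improvement. The stated recruitment rule gives a discretionary, workload-dependent convenience sample for a question about routine prevalence. The text at hand fixes no order of approach and no record of reasons for non-enrolment.

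The effect on the rate is unknown in size and direction and may be nil. Under the assumed range of k from 0.5 to 2, it would be minor if nearly all patients are enrolled and substantial if few are. The conclusion does not depend on any of those values. It rests on the mismatch between objective and sampling rule, and on the fact that unrecorded reasons cannot be reconstructed later. It is subject to the limit that later sections of the form are not shown.

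**What to change.** In section 3(b):

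1. Replace the discretionary choice with a rule: whenever a device is free, approach the next scheduled FDG patient. Allow a pass-over only to avoid delaying care.
2. Keep a de-identified count of scheduled FDG patients who are not approached or who decline, with the reason: no time, no device, declined, or other.
3. Report that count beside the infiltration rate, and describe the rate as that of enrolled patients.

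The cost is a short log, possibly a minor IRB amendment, and slightly less recruitment flexibility. There is no additional procedure for patients. The protocol's own figures for the time added by participation are small: "add only 2-3 minutes to the current standard of care PET/CT scanning process" in section 1(b) and "should only add 5 minutes to the time of their PET/CT scan" in section 3(b). Neither says whether the consent discussion is included.

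The change does not remove selection. A free device is still needed, and the allowance for avoiding delay keeps some judgement about time. What it does is narrow that judgement and leave a record of how often, and why, it was used.
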